7.1 Definitions

Unanticipated Problems Involving Risk to Subjects or Others

Any incident, experience, or outcome that meets all of the following criteria:

- Unexpected in nature, severity, or frequency (i.e. not described in study-related documents such as the IRB-approved protocol or consent form, the investigators brochure, etc)
- Related or possibly related to participation in the research (i.e. possibly related means there is a reasonable possibility that the incident experience, or outcome may have been caused by the procedures involved in the research)
- Suggests that the research places subjects or others at greater risk of harm (including physical, psychological, economic, or social harm).

Adverse Event

An **adverse event** (AE) is any symptom, sign, illness or experience that develops or worsens in severity during the course of the study. Intercurrent illnesses or injuries should be regarded as adverse events. Abnormal results of diagnostic procedures are considered to be adverse events if the abnormality:

- results in study withdrawal
- is associated with a serious adverse event
- is associated with clinical signs or symptoms
- leads to additional treatment or to further diagnostic tests

- is considered by the investigator to be of clinical significance

Unanticipated Adverse Device Effect (UADE):

An unanticipated adverse device effect is any serious adverse effect on health or safety, or any life-threatening problem or death, caused by or associated with an investigational device. Internal Unanticipated Adverse Device Effects (UADE) reports must be made within 10 working days.

Adverse Event Reporting Period

The study period during which adverse events must be reported is normally defined as the period from the initiation of any study procedures to the end of the study treatment follow-up. For this study, the study treatment follow-up is defined as 90 days following hospital discharge from the ileostomy closure procedure

Preexisting Condition

A preexisting condition is one that is present at the start of the study. A preexisting condition should be recorded as an adverse event if the frequency, intensity, or the character of the condition worsens during the study period.

General Physical Examination Findings

At screening, any clinically significant abnormality should be recorded as a preexisting condition. At the end of the study, any new clinically significant findings/abnormalities that meet the definition of an adverse event must also be recorded and documented as an adverse event.

Post-study Adverse Event

All unresolved adverse events should be followed by the investigator until the events are resolved, the subject is lost to follow-up, or the adverse event is otherwise explained. At the last scheduled visit, the investigator should instruct each subject to report any subsequent event(s) that the subject, or the subject's personal physician, believes might reasonably be related to participation in this study. The investigator should notify the study sponsor of any death or adverse event occurring at any time after a subject has discontinued or terminated study participation that may reasonably be related to this study. The sponsor should also be notified if the investigator should become aware of the development of cancer or of a congenital anomaly in a subsequently conceived offspring of a subject that has participated in this study.

Abnormal Laboratory Values

A clinical laboratory abnormality should be documented as an adverse event if any one of the following conditions is met:

- The laboratory abnormality is not otherwise refuted by a repeat test to confirm the abnormality
- The abnormality suggests a disease and/or organ toxicity
- The abnormality is of a degree that requires active management; e.g. change of dose, discontinuation of the drug, more frequent follow-up assessments, further diagnostic investigation, etc.

Hospitalization, Prolonged Hospitalization or Surgery

Any adverse event that results in hospitalization or prolonged hospitalization should be documented and reported as a serious adverse event unless specifically instructed otherwise in this protocol. Any condition responsible for surgery should be documented as an adverse event if the condition meets the criteria for and adverse event.

Neither the condition, hospitalization, prolonged hospitalization, nor surgery are reported as an adverse event in the following circumstances:

- Hospitalization or prolonged hospitalization for diagnostic or elective surgical procedures for a preexisting condition. Surgery should **not** be reported as an outcome of an adverse event if the purpose of the surgery was elective or diagnostic and the outcome was uneventful.
- Hospitalization or prolonged hospitalization required to allow efficacy measurement for the study.

- Hospitalization or prolonged hospitalization for therapy of the target disease of the study, unless it is a worsening or increase in frequency of hospital admissions as judged by the clinical investigator.

7.2 Recording of Adverse Events

At each contact with the subject, the investigator must seek information on adverse events by specific questioning and, as appropriate, by examination. Information on all adverse events should be recorded immediately in the source document, and also in the appropriate adverse event module of the case report form (CRF). All clearly related signs, symptoms, and abnormal diagnostic procedures results should be recorded in the source document, though should be grouped under one diagnosis. The monitoring period for Serious Adverse Events (SAE) will continue for 6 months after the study procedure.

All adverse events, including those possibly related, occurring during the study period must be recorded. The clinical course of each event should be followed until resolution, stabilization, or until it has been determined that the study treatment or participation is not the cause. Serious adverse events that are still ongoing at the end of the study period must be followed up to determine the final outcome. Any serious adverse event that occurs after the study period and is considered to be possibly related to the study treatment or study participation should be recorded and reported immediately.

7.3 Reporting of Unanticipated Adverse Device Effects and Unanticipated Problems

Investigators and the protocol sponsor must conform to the reporting timelines, formats and requirements of the various entities to which they are responsible, but at a minimum those events that must be reported are those that are:

- Related, or possibly related, to study participation,
- unexpected, and
- serious or involve risks to subjects or others (see definitions, section 7.1).

If the report is supplied as a narrative, the minimum necessary information to be provided at the time of the initial report includes:

- | | |
|------------------------------|--|
| • Study identifier | • Current status |
| • Study Center | • Whether study treatment was discontinued |
| • Subject number | • The reason why the event is classified as serious |
| • A description of the event | • Investigator assessment of the association between the event and study treatment |
| • Date of onset | |

7.3.1 Investigator reporting: notifying the Dartmouth IRB

This section describes the requirements for safety reporting by investigators who are Dartmouth faculty, affiliated with a Dartmouth research site, or otherwise responsible for safety reporting to the Dartmouth IRB. The Dartmouth College IRB (CPHS) requires expedited reporting of those events related to study participation that are unforeseen and indicate that participants or others are at increased risk of harm. The Dartmouth IRB will not acknowledge safety reports or bulk adverse event submissions that do not meet the criteria outlined below. The Dartmouth IRB requires researchers to submit reports of the following problems within 10 working days from the time the investigator becomes aware of the event:

- Any adverse event (regardless of whether the event is serious or non-serious, on-site or off-site) that occurs any time during or after the research study, which in the opinion of the principal investigator is:

Unexpected (An event is “unexpected” when its specificity and severity are not accurately reflected in the protocol-related documents, such as the IRB-approved research protocol, any applicable investigator brochure, and the current IRB-approved informed consent document and other relevant sources of information, such as product labeling and package inserts.)

AND

Related to the research procedures (An event is “related to the research procedures” if in the opinion of the principal investigator or sponsor, the event was more likely than not to be caused by the research procedures.)

Reporting Process

Unanticipated problems posing risks to subjects or others as noted above will be reported to the Dartmouth IRB using the form: “Unanticipated Problems Posing Risks to Subjects or Others Including Reportable Adverse Events” or as a written report of the event (including a description of the event with information regarding its fulfillment of the above criteria, follow-up/resolution and need for revision to consent form and/or other study documentation). Internal Unanticipated Adverse Device Effects (UADE) reports must be made within 10 working days.

Copies of each report and documentation of IRB notification and receipt will be kept in the Clinical Investigator’s study file.

7.4 Stopping Rules

1. Should a patient participating in the study suffer an adverse event resulting in mortality or severe morbidity such as necrotizing infection or sepsis as a result of mesh infection, the trial will be suspended pending an investigation by the Principal Investigator and the co-investigators as to whether the procedure or prosthetic mesh was the inciting cause of the adverse effect.
2. Should a patient require return to the operating room for treatment of a wound occurrence requiring removal of the mesh, the trial will be suspended pending investigation of the case to determine the cause of the wound occurrence as well as to evaluate the necessity of modification of the protocol to avoid similar occurrences in future patients.
3. If either of the above conditions occur, in addition to stopping the trial, both the CPHS and NCCC DSMAC will be promptly notified.

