1.4 Risk/Benefits

The primary concern is for surgical site occurrences. In the absence of mesh, the incidence of infection in ileostomy closures is estimated between 6 and 18%.⁴³⁻⁴⁵ This rate is minimized with the use of a purse string skin closure with iodine impregnated gauze packing vs partial closure with an open ended drain (Penrose type) or primary skin closure.⁴⁶ Prospective trial data estimates the overall incidence of infections when bioabsorbable mesh is placed in Class II and III ventral hernia repairs at 18%. None required mesh explantation and all wounds eventually healed.²⁷ Other reports of macroporous polypropylene mesh in clean-contaminated and contaminated wounds suggest an infection rate of 7.1% for clean contaminated and 19% for contaminated cases.²³ Surgical site occurrences will be treated on an individual patient basis determined by the clinical consequences of the occurrence. Infection may potentially be treated with antibiotics, local wound care, operative debridement, radiographically guided drainage procedures, vacuum assisted wound closure devices, or mesh removal at the discretion of the study team. Other potential adverse events are those inherent to intestinal surgery; anastomotic leak, peritoneal abscess formation, bowel obstruction, or ileus, in addition to the risks associated with general anesthesia.

2 Study Objectives

Primary Objective: To validate the technical procedure of mesh implantation at the time of ileostomy closure and preliminarily determine the incidence of surgical site occurrences (particularly those requiring intervention) compared to standard ileostomy closure technique.

Secondary Objective #1: Measure and compare quality of life scores for aspects related to the procedure to those related to bowel function.

Secondary Objective #2: To evaluate the process for longitudinally monitoring for the occurrence of hernia at site of stoma closure. We will evaluate our study protocol for the feasibility of performing a larger trial by measuring recruitment, retention of patients, adherence to the study protocol, and process assessment.

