3.3 Secondary Study Endpoints

The secondary endpoints will be evaluation of the incidence of hernia formation at the ileostomy site on a prospective basis at 30 days and 6 month intervals thereafter until two years from the date of ileostomy closure. The Promis SF 2.0 8a Ability to Participate in Social Roles and Activities instrument will be used to assess quality of life and the Colorectal Functional Outcome (COREFO) instrument will be used to evaluate bowel function at each interval.

4 Subject Selection and Withdrawal

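### The trigger and purpose clauses of stopping rule 1 (7.4) do not fit together: attribution to mesh infection is part of the trigger, although cause is what the suspension is meant to establish

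*Combined protocol and SAP*

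**What the plan says.** Section 7.4 has three rules.

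- **Rule 1, trigger and consequence:** "mortality or severe morbidity such as necrotizing infection or sepsis as a result of mesh infection, the trial will be suspended pending an investigation".
- **Rule 1, purpose:** the principal investigator and the co-investigators are to reach a finding "as to whether the procedure or prosthetic mesh was the inciting cause of the adverse effect".
- **Rule 2, trigger:** "Should a patient require return to the operating room for treatment of a wound occurrence requiring removal of the mesh".
- **Rule 2, purpose:** suspension "pending investigation of the case to determine the cause of the wound occurrence", and to consider whether the protocol needs changing.
- **Rule 3:** if rule 1 or rule 2 is met, CPHS (the Dartmouth IRB) and the NCCC DSMAC are told promptly.

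Section 1.4 separately lists risks of the bowel operation itself: "anastomotic leak, peritoneal abscess formation, bowel obstruction, or ileus, in addition to the risks associated with general anesthesia".

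Section 7.4 states no time window. Section 7.1 ends adverse event reporting 90 days after discharge from the closure admission. Section 7.2 continues monitoring of serious adverse events for 6 months after the procedure.

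**The concern.** A stopping rule should start from something the site can observe and leave cause to the review that follows. Rule 1 mixes the two. Its trigger contains a causal finding, and its investigation is then asked to make a causal finding. The two findings also differ in scope: the trigger names mesh infection only, while the inquiry covers the procedure as well as the mesh.

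Take, as an illustration, a patient who becomes septic soon after surgery with an intra-abdominal collection. The site may have to decide whether the mesh is infected before it knows whether rule 1 applies. If it attributes the sepsis to an anastomotic leak, rule 1 may not be met, although whether the modified operation contributed is a question the inquiry was meant to answer. The protocol does not define mesh infection, so this first judgement has no stated criteria.

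At stake is whether the next patient receives a permanent implant before a death or life-threatening event has been examined, and whether different people would apply the rule alike.

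**Working it through.** Rule 1 is a single-event, qualitative trigger. It has no rate, threshold, alpha or power, so there is no figure of the plan's own to reproduce. The check is a comparison of texts.

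**Step 1. What the causal qualifier attaches to.** The sentence allows at least three readings. The entries show whether rule 1 requires suspension.

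| Qualifier attaches to | Death of unknown or other cause | Necrotizing infection not attributed to mesh | Sepsis not attributed to mesh infection |
|---|---|---|---|
| The whole phrase (narrow) | Not required | Not required | Not required |
| Both examples (broader) | Required | Judgement | Judgement |
| Sepsis only (broader) | Required | Required | Judgement |

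Judgement means that the event is not one of the named examples, but because the list is illustrative the site could still class it as severe morbidity. On every reading the qualifier forms part of the trigger for at least sepsis.

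**Step 2. Trigger against purpose.** A severe event caused by the procedure without mesh infection lies within the question the inquiry must answer. On the narrow reading it never starts the inquiry.

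**Step 3. Rule 1 against rule 2.** Rule 2 is triggered by an observable event, a return to theatre with mesh removal, and determines cause afterwards. Rule 1 does not follow that order.

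**Step 4. Does any other provision require a pause?**

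- Rule 2 applies only if mesh is removed for a wound occurrence.
- The stage 1 gate (3.1) counts only wound occurrences that need a return to theatre, allows one of them, and governs the move to stage 2 after the first five patients.
- Expedited IRB reporting (7.3.1) requires the event to be unexpected and judged more likely than not caused by the research procedures. It is a report, not a pause. Leak and abscess are named in 1.4, so they may also fail the first condition.
- Prompt notification under rule 3 depends on rule 1 or rule 2 being met.
- The DSMAC may suspend (9.1), at its discretion, and reviews this protocol quarterly.

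None requires a pause for a death or severe event of unknown or other cause.

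**Step 5. Exposure between reviews.** Inputs: 20 patients, a planned period of 1 year, and 35 to 40 likely eligible patients a year (all from 6.1 to 6.2); quarterly review (9.1). At the planned pace, assuming even accrual, 20/4 = 5 patients per quarter. If every eligible patient enrolled, 35/4 = 8.75 to 40/4 = 10 per quarter. These rates bear mainly on stage 2, whose 15 patients are followed concurrently; the first five are treated and followed sequentially.

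**Step 6. Time window.** The events in rule 1 are serious, so both the 90 days in 7.1 (counted from discharge) and the 6 months in 7.2 (counted from the procedure) could be taken to bound it. Rule 1 cites neither.

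**The case against.** The best defence is grammatical. The two examples are introduced as illustrations, and the qualifier most naturally belongs to them rather than to death or severe morbidity in general. The purpose clause supports this: an inquiry into the procedure as well as the mesh makes little sense if only mesh infection could start it. On that view a death of unknown cause does suspend the trial, and sepsis from another source can still be classed as severe morbidity. This stands in part. The documents do not support saying that every death not attributed to the mesh is outside the rule. But the argument turns on intention, not on what the sentence requires, and it still leaves non-mesh sepsis to judgement.

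Existing controls also narrow the gap. Section 3.2 counts organ space infection as a wound occurrence, so an intra-abdominal collection might count at the stage 1 gate or under rule 2. The principal investigator has continuing safety oversight (7.5), and the DSMAC can act. These are partial or discretionary; none requires a pause.

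Three stronger inferences are tempting and should not be drawn:

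- **That any cancer death during follow-up would suspend the trial.** Hernia follow-up runs at "6 month intervals thereafter until two years from the date of ileostomy closure", but the trigger is an adverse event, and 7.1 and 7.2 set much shorter windows. Accrual is also planned for one year, so later deaths could come after the last implantation. What is missing is a cross-reference to a window. No probability of suspension can be derived from the documents, which give no mortality rate.
- **That every bowel complication in 1.4, or the fistula rate in 1.3.1, counts as an uncovered event.** Ileus or obstruction is not in itself death or severe morbidity, and the fistula rate comes from a trial of ventral hernia repair.
- **That rule 2 is also defective.** Its trigger and purpose are consistent.

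**Conclusion.** The concern holds as an inconsistency within rule 1. The causal qualifier in the trigger does not match the wider causal question that the suspension is meant to answer. On the narrow reading, deaths and septic events of unknown cause, or attributed to the bowel procedure, fall outside mandatory suspension and outside prompt notification. On the broader readings death is covered, and the gap shrinks to severe infection from another source, which is left to judgement.

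The size is qualitative. The documents give no event rate from which to say how often the gap would matter. The figure of about 5 further patients between quarterly reviews assumes even accrual and no discretionary action by the investigators or the DSMAC; it describes exposure, not expected harm. The conclusion depends neither on that figure nor on choosing one reading: the wording permits more than one, and they give different answers for the same event. For a pilot of a permanent implant in which preliminary safety is part of the primary objective, this is worth correcting.

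**What to change.** Reconcile the two clauses of 7.4, rule 1, so that an observable event starts the pause, and attribution to mesh or procedure is left to the investigation. Rule 2 already has this structure and needs no change. Notification under rule 3 will then follow the same observable event.

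State in rule 1 which existing window applies, and reconcile the 90 days after discharge in 7.1 with the 6 months after the procedure in 7.2, including their different starting points.

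Which clinical events belong in the trigger is for the investigators and the DSMAC to decide; this review proposes none. The change is one of protocol wording, with no effect on sample size or data collection. Its downside is an occasional short pause for an event later judged unrelated.

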3.2 Primary Study Endpoints

The primary end point of the study is the validation of the mesh implantation procedure. We will assess the incidence of wound occurrences (defined as S-SSI, D-SSI, organ space SSI, dehiscence, and seroma formation) at 30days, with particular attention to wound occurrences requiring procedural intervention, including but not limited to, operative debridement, radiographically guided drain placement, or excision of the mesh. These incidences will be compared to historical controls.

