4.4 Early Withdrawal of Subjects

4.4.1 When and How to Withdraw Subjects

Patients may be withdrawn from the study at any time based upon withdraw of consent. Patients may also be withdrawn if the study treatment cannot be tolerated (i.e. removal of mesh device is required). Patients must continue to participate for 30days post-operatively in order for inclusion in the analysis of the primary endpoint data.

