9.1 Safety and Data Monitoring

This study will be monitored by the Data Safety Monitoring and Accrual Committee (DSMAC) of the Norris Cotton Cancer Center. It is a multidisciplinary committee charged with overseeing monitoring of safety of participants, conduct, progress, and validity and integrity of the data of all clinical trials at NCCC at Dartmouth. The Committee meets quarterly to review accrual rates and information for studies that have accrued participants. The Clinical Cancer Review Committee (CCRC) determines the frequency of DSMAC data and safety review. This protocol will be reviewed on a quarterly basis. The DSMAC has the authority to suspend or to recommend termination to the CCRC of all research activities that fall within its jurisdiction. In the event that a study is suspended or terminated, that information will be forwarded to the CPHS (Dartmouth IRB) office.

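### Stopping rule 2 pauses the trial after mesh removal only when the reoperation treats a wound occurrence; tying the pause to the removal itself would close a small gap

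*Combined protocol and SAP*

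**What the plan says.** Section 7.4 has three rules. Rule 1 suspends the trial for death or "severe morbidity such as necrotizing infection or sepsis as a result of mesh infection". Rule 2 suspends it under the condition "Should a patient require return to the operating room for treatment of a wound occurrence requiring removal of the mesh", so that the cause can be established and the protocol changed if needed to protect later patients. Rule 3 applies when rule 1 or rule 2 is met: "both the CPHS and NCCC DSMAC will be promptly notified".

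Section 7.4 does not define wound occurrence. The only express definition is in section 3.2, in the sentence on 30-day incidence: "wound occurrences (defined as S-SSI, D-SSI, organ space SSI, dehiscence, and seroma formation". The primary objective in section 2 uses a different term, the "incidence of surgical site occurrences (particularly those requiring intervention) compared to standard ileostomy closure technique". Section 1.3.1 gives a longer list for surgical site occurrences, including enterocutaneous fistula, when it describes a cited trial.

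Mesh removal also appears in section 4.4.1, with a consequence for the patient only: "Patients may also be withdrawn if the study treatment cannot be tolerated (i.e. removal of mesh device is required". On oversight, section 9.1 says "The DSMAC has the authority to suspend or to recommend termination to the CCRC" and "This protocol will be reviewed on a quarterly basis".

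**The concern.** Rule 2 has three conditions: a return to the operating room, removal of the mesh, and a wound occurrence as the reason. The third depends on how the indication is labelled. If the section 3.2 list governs, a mesh taken out for erosion, fistula, obstruction or pain can fall outside rule 2. Unless it is also judged severe morbidity, it falls outside rule 1, and rule 3 then does not apply either.

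What is at stake is whether the pause and the prompt notice follow automatically. This is a 20-patient pilot of a permanent implant in a use that section 1.1 calls novel, and its primary endpoint is validation of the implantation procedure. A removal for a cause connected with the mesh or the stoma site bears on whether to continue unchanged, which is the question rule 2 exists to ask. The investigators who would classify the indication would also decide whether the rule applies.

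**Working it through.** The plan states no figure for its stopping rules, so there is none to reproduce. The check compares the provisions for one case: the mesh is removed at reoperation, the indication is not classed as infection, dehiscence or seroma, and the event is not judged severe morbidity.

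| Provision | What sets it off | Forces a pause in this case? |
|---|---|---|
| 7.4 rule 1 | Death or severe morbidity (the examples are illustrative) | No, by the terms of the case |
| 7.4 rule 2 | Reoperation for a wound occurrence, with mesh removal | No on the 3.2 list; possibly yes on a broader reading |
| 7.4 rule 3 | Rule 1 or rule 2 met | No |
| 3.1 first-phase gate | More than one wound occurrence needing reoperation among five patients | No; it uses the same term |
| 4.4.1 withdrawal | Treatment not tolerated, glossed as mesh removal | No; it permits withdrawal of the patient |
| 7.3.1 IRB and device-effect reporting | Unexpected and related events, or unanticipated device effects, within 10 working days | No; it is a report only |
| 9.1 DSMAC | Quarterly review | No; it may suspend at its discretion |

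The reporting route in 7.3.1 also requires an adverse event to be unexpected. Section 1.1 names erosion, adhesions, fistula and pain as historical concerns with mesh, so such an event could be judged expected and not reportable by that route.

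**Which definition governs.** With the 1.3.1 list in place of the 3.2 list, fistula is covered. Mesh erosion, obstruction and pain are still not named.

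**Scale.** Inputs: N = 20 (Study Summary and section 6) and a mesh removal rate of 4% (section 1.3.1, from contaminated ventral hernia repair).

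- Expected removals of any cause: 20 × 0.04 = 0.8.
- Chance of at least one, if the rate carried over: 1 − 0.96^20 = 0.558.
- Expected removals in the gap, for a share f of all removals: 0.8 × f. The documents give no f. As pure assumptions, f = 5%, 10% and 25% give 0.04, 0.08 and 0.20.

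These counts have no time limit, whereas a pause protects someone only while implants remain to be done. Section 6 plans 20 patients in one year, so 20 / 4 = 5 implants could fall between two quarterly DSMAC reviews. At the 80% recruitment target of section 2 applied to 35–40 eligible patients a year, the pace is 28–32 a year, or 7–8 a quarter. Both are worst cases for the second phase, because the first five patients are treated and followed one after another. They also assume that neither the investigators nor the DSMAC act sooner.

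**The case against.** The strongest reply is that the gap is narrow and rests on a reading that section 7.4 does not impose.

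- The 3.2 list sits in a 30-day endpoint sentence. Section 7.4 does not cite it and has no 30-day limit.
- Section 1.4 mentions mesh removal as one treatment for infection while discussing surgical site occurrences, which favours reading rule 2 more widely.
- Rule 1 is open-ended, and its investigation asks whether the procedure or the mesh was the cause, without limiting this to infection. A reoperation for mesh-related fistula or obstruction could well be judged severe.
- An infected fistula or erosion can be classed as an organ space infection.
- The technique in section 5.2 closes or bridges the posterior sheath to keep mesh away from bowel.
- This is one centre with three surgeons, and the principal investigator is responsible for safety.
- Section 1.4 also reports a prospective study with no explantations, though with bioabsorbable mesh.

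All of this stands as to size. It leaves mainly removals for pain, or for milder or uninfected complications. It does not show that any clause forces a pause for them.

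A reader might infer more than the documents support in three ways:

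- *That serious fistulas or erosions would pass without a pause.* Most would probably be caught by the routes above.
- *That 4.4.1 already provides a removal-based trigger regardless of indication.* It is permissive, framed as intolerance, and concerns the patient; it is a weak precedent.
- *That 0.8 is a ceiling.* It is an expected count at a rate borrowed from another operation.

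**Conclusion.** The gap is real but minor. On its wording, rule 2 does not pause the trial after every mesh-related removal, and no other provision forces the pause. The conclusion rests on two conditions: that the 3.2 definition, or another reading that leaves out the indication, is applied to section 7.4, and that the event is not judged severe morbidity under rule 1.

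The frequency cannot be derived. The 4% rate comes from ventral hernia repair, and the share of removals in the gap is not given, so neither the assumed shares nor the quarterly implant counts should be read as estimates of risk. The documents do not support saying that such events are likely, or that the trial is unsafe as written. The case for acting is that an existing rule can serve its stated purpose better at little cost.

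**What to change.** Reword rule 2 in section 7.4 along these lines: *If the study mesh is removed at a return to the operating room, other than a documented incidental removal at reoperation for a condition unrelated to the mesh or the stoma site, the trial will be suspended pending investigation of the cause of the removal and of whether the protocol needs modification.* Keep rules 1 and 3 as they are.

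A narrower alternative is to define wound occurrence in section 7.4 by the 1.3.1 list. That would settle fistula, but erosion, obstruction and pain would remain unnamed and the pause would still depend on a label.

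The cost is one amended rule, handled by the existing investigators, CPHS and DSMAC, with no change to treatment or sample size. The downside is a rare, brief extra suspension, at a rate the documents do not allow to be estimated. The exception for incidental removals avoids halting the trial for clearly unrelated reoperations. Once enrolment has closed, the change affects only investigation and notice.
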